3.0 PATIENT/SAMPLE SELECTION

Every patient that is scheduled to get a PET-CT at UH Case Medical Center either for preoperative high-grade rectal cancer or for colorectal cancer follow-up will be invited to join this pilot study. Initially, 10 patients per group will be invited to participate. We expect to recruit this number of patients in a two year period at the most.

Inclusion Criteria:

- Either having a T3 (The cancer has grown through the muscularis propria and into the outermost layers of the colon or rectum but not through them) or higher, node positivity or metastatic lesion in the context of rectal cancer or being studied for colorectal cancer follow up, independent of the renal function
- PET-CT should be requested by a referring physician. In the case of having an MR requested as well, it will be reported from the MRI images generated in the PET-MRI
- Stable physical medical conditions to undergo a MRI

- Informed consent must be given and signed prior to study enrollment
- Patient should be over 21 years old

Exclusion Criteria

- Refuse to give and/or sign the informed consent
- Subjects who do not meet the above mentioned inclusion criteria
- Subjects who have a pacemaker
- Subjects who have a metallic prostheses either in the pelvis or in the abdomen that will interfere with the MR imaging of that anatomical area
- Subjects who suffer from claustrophobia
- Pregnant women
- Cognitive impairment that affects the subjects ability to give consent

4.0 REGISTRATION PROCEDURES

The potential participant will be informed of the ongoing protocol during the visit to his referring physician where he will also be provided the consent form. He/She will then be formally invited to participate in this research study at the time of the appointment for the diagnostic PET-CT examination. A member of the research team will provide all information and answer questions related to the planned study. This study member will also screen the potential candidate for the inclusion and exclusion criteria. The candidate subject will only qualify for the participation in the study if meeting all inclusion/exclusion criteria as listed in Sections 3.2 and 3.3. The patient will then first be screened for MRI safety using the standard MRI informed consent form as typically used for all diagnostic MRI as a standard of care at UHCMC.

If the candidate subject is confirmed to meet the inclusion/exclusion criteria and to qualify for safety features for a diagnostic MRI scan and is interested in participating, the Informed Consent form will be given to the patient. The patient will have the opportunity to discuss the Informed Consent Form with family or friends from the time he/she is consented to the time of the examination.

The study team member will then obtain the permission from the patient to participate. The member of the research team will go over the informed consent form with the candidate subject.

5.0 RESEARCH PLAN

5.1 Study procedures and data analysis plan

Patients who enroll in this study will receive their clinically requested diagnostic PET-CT and a PET-MRI. When a diagnostic MRI is additionally requested, a report will be generated from the MRI images obtained in the PET-MRI. Both exams will be performed at the Seidman Cancer Center as part of their normal diagnostic care and will meet all of the institutionally imposed criteria for these studies. For research purposes, additional MR sequences that are completely harmless to the patient, but haven't yet been FDA approved for the clinical arena, will be performed. If any additional relevant information is discovered because of these latter sequences proper communication of these findings to the referring physician will be done.

Using the same F18-FDG injection PET-MRI will be performed, before or after the clinically requested PET-CT. If an MRI has also been requested, the report will be generated from the MRI images performed in the same scanner as the PET-MRI. After completion of the first scan, be it the PET-MRI or the PET-CT, the patient will immediately undergo the other examination. No additional F18-FDG injection will be required. MR contrast agents may be injected if it's requested by the referring physician and there are no contraindications. As a preparation for the MRI examination, all subjects except those with prior rectal surgery will receive a small amount of rectal gel to allow enhanced lesion detection. Intramuscular glucagon (1 mg) will be administered to all subjects to help relax the bowels during the MRI examination, unless there are contraindications to it which include history of glucagon hypersensitivity or pheochromocytoma. If the MRI is clinically ordered, the rectal gel and glucagon administrations are standard of care. However, they are research if the MRI is not ordered by the referring physician.

The patient will be inside the PET-MRI scanner for approximately 60-90 minutes whether or not an MRI is performed.

All the imaging data obtained from the patient will be stored in the Radiology Department research PACS after a unique code that links the patient to its identifiers is assigned by a CREC-trained certified co-investigator. All the clinically requested exams will be archived in the Department of Radiology clinical PACS system. Similarly, the PI's and Co-PI's reports that are generated from the clinical images obtained will be permanently archived in Radiology's IDX medical record system. If after reviewing the research data, a finding not previously seen in the clinical images, becomes apparent appropriate steps will be taken to inform the patients referring physician.

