2.0 OBJECTIVES

Our objective is to test the diagnostic performance of PET-MRI in two different settings. The first setting is the staging of preoperative high-grade rectal cancer patients, defined by T3 stage or higher or N1 stage or higher or presence of metastasis, that are referred to PET-CT and MRI. In this population Pathology will be the gold standard when available for local staging and PET/CT for M staging. When Pathology is not available, both MRI and PET/CT results will be used to determine T and N stage.

The second setting is the follow up of colorectal cancer patients that are referred to PET-CT with or without a diagnostic MRI request by their physicians. In this second group the gold standard for recurrence will be obtained from analyzing CEA levels and PET/CT and MRI results. Pathology results will be used as well whenever available.

A secondary objective is to test different attenuation correction MR sequences and novel diagnostic MR sequences.

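### In the follow-up group nothing ensures that a recurrence missed by both scans and by CEA is found, so the sensitivity and NPV of both scans tend to be overstated

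*Combined protocol and SAP*

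**What the plan says.** Section 2.0 defines the reference for the follow-up group in two sentences: "the gold standard for recurrence will be obtained from analyzing CEA levels and PET/CT and MRI results", and then "Pathology results will be used as well whenever available". It does not say when these results must be obtained, how they are combined, or what CEA level counts as recurrence.

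Section 5.1 gives two routes by which research findings reach the treating side. For the additional MR sequences: "If any additional relevant information is discovered because of these latter sequences proper communication of these findings to the referring physician will be done". For later review of the research data, if "a finding not previously seen in the clinical images, becomes apparent appropriate steps will be taken to inform the patients referring physician". The PET-CT is clinically requested and so is reported in any case. Where an MRI was also ordered, its report is made from the PET-MRI images.

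Section 8.0 plans sensitivity, specificity, both predictive values and accuracy for each scan, with 95% confidence intervals, from standard formulas against the criterion standard. It compares the scans by McNemar's test. It has no adjustment for unequal verification. No section sets a follow-up window or later outcome check for patients whose scans are negative.

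**The concern.** Tissue is seldom taken without a reason, and in this plan the main visible reason is a positive scan. A patient positive on either scan may therefore be checked by pathology. A patient negative on both has only CEA, or pathology prompted by something unrelated. If both are silent, the patient enters the accuracy table as recurrence-free.

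Shared misses are plausible. Section 5.1 runs the two scans back to back on a single F18-FDG injection, so a lesion with low uptake may escape the PET component of both.

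This is separate from the problem that PET/CT and MRI results are themselves part of the reference. Taking the scans out of the reference would still leave pathology obtained mainly in scan-positive patients. What is at stake is the absolute sensitivity and NPV of each scan. The planned confidence intervals would not reflect the bias.

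**Working it through.** The plan has no figure to reproduce. Section 8.0 bases the sample size on funding, Section 3.0 gives 10 patients per group initially, and no sensitivity, recurrence rate or CEA detection rate is stated. Every rate below is an assumption.

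**Apparent sensitivity.** Let Se be the true sensitivity of a scan, q the share of recurrences missed by both scans, and u the share of those that CEA also fails to flag. Assume that every scan-positive recurrence is confirmed, that a CEA flag leads to the patient being counted as a recurrence, and that unflagged double-negatives are counted recurrence-free. A fraction q × u of true recurrences then drops out of the denominator:

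apparent Se = Se / (1 − q × u)

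Take Se = 0.75 for each scan. Independent misses give q = 0.25 × 0.25 = 0.0625, and q cannot exceed 0.25.

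| q | u | Calculation | Apparent Se | Excess (points) |
|---|---|---|---|---|
| 0.0625 | 0.4 | 0.75 / 0.975 | 76.9% | 2 |
| 0.0625 | 1.0 | 0.75 / 0.9375 | 80.0% | 5 |
| 0.10 | 0.4 | 0.75 / 0.96 | 78.1% | 3 |
| 0.15 | 0.7 | 0.75 / 0.895 | 83.8% | 9 |
| 0.20 | 1.0 | 0.75 / 0.80 | 93.8% | 19 |

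If CEA flags every shared miss (u = 0), there is no excess.

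**NPV.** Assume 40% prevalence of recurrence, q = 0.15, and 90% of disease-free patients negative on both scans. The true NPV of a double-negative result is 0.6 × 0.9 / (0.6 × 0.9 + 0.4 × 0.15) = 0.54 / 0.60 = 90%. The recorded value is (0.54 + 0.06 × u) / 0.60, which is 94% at u = 0.4 and 100% at u = 1. The NPV of each scan separately moves in the same direction.

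**Comparison of the scans.** Both sensitivities are divided by the same 1 − q × u, so their ratio does not move. With assumed true values of 0.80 and 0.90, q = 0.10 and u = 1, they become 0.889 and 1.000. The ratio is 1.125 before and after, and the difference grows only from 10 to 11 points. Double-negatives are concordant, so McNemar's discordant counts do not change.

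**Ten patients.** The chance of at least one hidden recurrence is 1 − (1 − prevalence × q × u)^10. At 40% prevalence it is:
- q × u = 0.025: 1 − 0.990^10 = 10%
- q × u = 0.04: 1 − 0.984^10 = 15%
- q × u = 0.105: 1 − 0.958^10 = 35%
- q × u = 0.20: 1 − 0.920^10 = 57%

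One such case would turn 3/4 = 75% (exact 95% interval 19% to 99%) into 3/3 = 100% (29% to 100%).

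**The case against.** The strongest reply is that this is a pilot whose main interest is PET-MRI against PET-CT, and that comparison survives. That stands, provided all positives are verified. The plan does not guarantee this, because the steps after a reported finding are undefined. It is also true that sampling error at this size is far larger than most of the biases in the table. But the plan does report absolute sensitivity and NPV, and an interval around a biased estimate gives no warning of the bias.

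Several stronger readings are tempting and are not supported.

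- A reader might infer that shared misses can never come to light. CEA is part of the reference and does not depend on the scans, and pathology prompted by any cause would count. The accurate statement is that no defined route or window ensures detection.
- A reader might infer that pathology becomes the gold standard for recurrence. In this group it joins a composite. Only in the staging group does Section 2.0 rank it first: "Pathology will be the gold standard when available for local staging and PET/CT for M staging".
- A reader might blame the reporting of research findings. Shared misses would stay hidden without it. The reporting protects patients, and PET-CT findings can prompt work-up just as well. That pathology follows a reported finding is a reasonable inference, not something the protocol states.
- A reader might infer that patients are classified on the day of the scan. Section 2.0 leaves the timing open.

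The rates are also open to challenge. The upper end needs strongly overlapping misses (20% out of a possible 25%) and a CEA that detects none of them.

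**Conclusion.** The point holds as a bias in absolute accuracy in the follow-up group. It arises from the reference rule in Section 2.0 together with the unadjusted formulas in Section 8.0. Followed as written, the plan tends to overstate the sensitivity and NPV of both scans whenever some recurrences are missed by both and by CEA. Under the assumed rates the excess in sensitivity is about 2 to 19 points, or about 2 to 5 points if the two scans miss independently. The direction does not depend on those rates; the size does. The documents do not support a claim that the bias favours PET-MRI over PET-CT.

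**What to change.** In Section 2.0, for the follow-up group, state that recurrence status will be taken from the medical record (pathology, later imaging and later CEA) at one prespecified interval after the study scans, the same for scan-positive and scan-negative patients. The sponsor chooses the interval. Record what prompted each pathology result. In Section 8.0, add that accuracy will also be reported by type of verification. Leave the reporting of findings to the referring physician as it is.

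A further table that leaves out pathology prompted by PET-MRI should not be added. It would discard the proof for exactly those lesions that only PET-MRI detected.

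The cost is protocol wording, a later review of about 10 charts, and a delay of follow-up group results by the chosen interval. No scan, visit or biopsy is added. Section 5.2 keeps the linking key for three years after study completion, so records can be traced.

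The limits should be stated. Recurrences that arise newly within the interval may be counted as misses, and later work-up may still depend partly on the scan results. The sponsor should also confirm that consent covers later record review, because the consent pages were not available here.

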5.2 Risks

The risks associated with the PET/MRI scan are the same risks as those posed by individual PET and MRI scans. A known risk related to MRI examinations is that the MRI magnet could attract certain kinds of metal that may cause injury to the patient. In order to avoid that, patients will be screened for any hazardous metal object that they may have or is implanted inside their body which includes heart pacemakers, intracranial aneurysm clips, heart valve prostheses and other implanted devices that are not compatible with MRI. Although there is no risk from ionizing radiation with MRI, subjects will be exposed to strong magnetic fields and radiofrequency pulses common to clinically used MRI systems, neither of which are associated with any known detrimental health effects.

Some of the experimental MR sequences that will be performed are not yet approved by the FDA for clinical use or have been partially approved for a certain type of surface coil in our scanner. These are already being used in a research setting and during clinical workup of patients outside the USA(11) without evidence of any adverse events.

For some types of MRI scans, when clinically indicated and requested by the physician, MR contrast agents may be used to enhance the MR images. These contrast agents to be used are approved by the FDA, are commercially available, and are used within label indications. With these contrast agents there is a risk of an allergic or fibrotic reaction which

occurs more often with x-ray contrast than with MRI contrast agents. Every effort will be made to minimize the risk of such reactions in this study by not exposing subjects who have a history of kidney disease (GFR >30mg/min), which is the cohort who most frequently exhibits fibrotic reactions, to these contrast agents. Generally, an intravenous injection of 10-20 ml will be used provided that the subject has no known reaction to contrast agents used in previous MRI scans. As with all such injections, bleeding, bruising, dizziness, fainting or infection may occur. Also, the injection may be painful but the discomfort should be brief and efforts will be made to minimize the pain. These risks, however, are part of the patient's clinical care and not a consequence of the research.

The MRI scanner makes a loud buzzing sound during the exam that could affect a patient's hearing. In order to protect patient from this sound, they will be provided earplugs during the exam. There might also be some claustrophobia-related discomfort involved with being required to lie still in a small space. If this occurs, patients can signal the technologist attending the MRI/PET who will terminate imaging immediately. The subject will be removed from the MRI machine and regarded as being withdrawn from the study. In effect, the screening process for the MRI portion of PET/MRI imaging will be the same as that done with clinical MRI. The risks associated with a PET scan include radiation exposure from the radioactive tracer. However, additional injection of a radiopharmaceutical is not required for the proposed study since patients will have been injected for their clinical PET scan. Thus, participation in this study does not expose subjects to additional ionizing radiation.

Finally, there is the potential risk of breach of confidentiality. To diminish this risk, we will assign each patient a unique study code that will link data to patient identifiers and the key will be stored separately. Deidentification will take place while transferring the images to the research PACS and will be performed by a CREC-trained certified co-investigator. The key connecting deidentified data to the patient will be generated at that same moment by the same co-investigator and stored in a laptop with an encrypted hard drive for three years after completion of the study, after which it will be destroyed. Only the PI and the co-investigator in charge of deidentifying patient data will have access to that computer that will be kept by the PI in his office.

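### The renal cut-off for withholding MR contrast in Section 5.2 has its inequality reversed and carries a unit that is not a filtration rate

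*Combined protocol and SAP*

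**What the plan says.** Section 5.2 (Risks) commits the study to limiting allergic and fibrotic reactions to MR contrast by "not exposing subjects who have a history of kidney disease (GFR >30mg/min), which is the cohort who most frequently exhibits fibrotic reactions". The bracket supplies the only renal number in the document.

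The other relevant statements are these:

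- Section 3.0 enrols patients "independent of the renal function", and its exclusion list has no renal item.
- Section 5.1 says that "MR contrast agents may be injected if it's requested by the referring physician and there are no contraindications". It does not say what those contraindications are, although the same paragraph does so for glucagon: "contraindications to it which include history of glucagon hypersensitivity or pheochromocytoma".
- Section 5.1 adds that the examinations "will meet all of the institutionally imposed criteria for these studies".
- Section 5.2 says the contrast agents "are used within label indications", and that "the screening process for the MRI portion of PET/MRI imaging will be the same as that done with clinical MRI".

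**The concern.** The words of the Section 5.2 sentence and its number point in opposite directions. The words identify people with kidney disease as those at highest risk and promise to keep contrast from them. The number describes people whose filtration is better than 30.

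Anyone who applied the number as printed would not withhold contrast from a kidney-disease patient with a GFR of 30 or less. Because enrolment is open whatever the renal function, such a patient can be in the study. What is at stake is a written safety threshold that fails to select the group it is meant to protect. No estimate, test or error rate depends on it.

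**Working it through.** The plan has no calculation to reproduce here. The check applies the printed criterion to example subjects and compares the result with the purpose stated in the same sentence.

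**Inputs.** The threshold (30), its direction (above) and its unit (mg/min) come from Section 5.2. The GFR values 25, 45 and 90 are illustrative and are not in the protocol.

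**Unit.** A filtration rate is a volume per time, such as mL/min. The printed unit is a mass per time. It is wrong whichever way the inequality points.

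**Direction.** The bracket can be read in two ways that give the number force:

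- Reading A, the bracket defines the group: withhold if GFR > 30.
- Reading B, the bracket narrows the group: withhold if there is a history of kidney disease and GFR > 30.

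The last two columns repeat A and B with the sign corrected to GFR < 30.

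| Subject | A, as printed | B, as printed | A, corrected | B, corrected |
|---|---|---|---|---|
| History, GFR 25 | given | given | withheld | withheld |
| History, GFR 45 | withheld | withheld | given | given |
| No history, GFR 45 | withheld | given | given | given |
| No history, GFR 90 | withheld | given | given | given |
| No history, GFR 25 | given | given | withheld | given |

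Here *given* means only that this criterion does not stop contrast; the other conditions in Sections 5.1 and 5.2 still apply.

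The first row is the decisive one. A patient with known kidney disease and a GFR of 25 is outside the printed number on both readings, and is inside it on both once the sign is corrected. As printed, that patient is covered only if the reader disregards the number and follows the words. The fourth row shows the same fault from the other side: on reading A, contrast would be withheld from a subject with a GFR of 90.

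**Is the threshold given correctly elsewhere?** No. Section 3.0 sets no renal limit. The contraindication clause, the institutional criteria, the labelling statement and the clinical MRI screening state no renal number.

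**Could it be an artefact of reading the PDF?** This is unlikely. The symbol reads cleanly, the surrounding words are intact, and a misread sign would not explain the wrong unit.

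**The case against.** The strongest reply is that this is a self-evident slip in a risk description and not an operating rule. Section 5.2 limits contrast to cases where it is clinically indicated and requested, and ends the paragraph by assigning contrast risks to routine clinical care and not to the research. The operative conditions are in Section 5.1, and nothing says that staff will use the Section 5.2 bracket as a checklist. A reader would have to ignore both the reference to kidney disease and the reference to the highest-risk cohort to be misled. If the words govern and the bracket is treated as a garbled gloss, the patient with a GFR of 25 is protected. Open enrolment is also compatible with safe practice, because contrast is optional.

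Most of this stands as a statement about likely harm, which is small. It is also fair to call the fault a drafting error and not a deliberate choice of design. It does not make the criterion right. The same paragraph makes a commitment to minimise these reactions in this study, and the bracket is the only figure attached to that commitment. A safety cut-off should not depend on the reader noticing that it is backwards.

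**Conclusion.** The concern holds. The inequality is reversed, the unit is not a filtration rate, and kidney-disease subjects with a GFR of 30 or less fall outside the printed number on either reading that gives the number force. No other section supplies a correct one.

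The conclusion rests on the wording of Section 5.2 and on GFR falling as renal function worsens. It assumes that 30 is the intended value and that only the sign and the unit are wrong.

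The size in subjects cannot be stated. The plan is for 10 per group in two groups, 2 × 10 = 20, and the documents do not say how many have impaired renal function or will receive contrast. The other safeguards limit practical harm, and sample size and analysis are unaffected. The text should be corrected because it is the protocol's only written renal threshold.

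**What to change.** In Section 5.2, change the bracket to GFR <30 mL/min, or to mL/min/1.73 m² if an indexed value is meant. The value 30 is the protocol's own.

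The investigators should confirm three things that the documents do not settle: the cut-off itself, the unit, and what happens at exactly 30, which a strict inequality in either direction leaves outside. While editing, they could also state whether the bracket defines kidney disease or narrows it. That decides whether a subject with no recorded history but a low GFR is covered, and whether contrast is permitted in known kidney disease with a GFR above 30.

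The cost is a one-line text correction, with no effect on enrolment, sample size or analysis.
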